Intrathecal Morphine versus Bilateral Quadratus Lumborum Blocks for Perioperative Analgesia in Pediatric Patients Undergoing Open Lower Abdominal Procedures: A Prospective Randomized Trial

NCT05506930

July 13, 2023

PROTOCOL TITLE:

Intrathecal Morphine versus Bilateral Quadratus Lumborum Blocks for Perioperative Analgesia in Pediatric Patients Undergoing Open Lower Abdominal Procedures: A Prospective Randomized Trial

PRINCIPAL INVESTIGATOR:

[name].

- **Objectives / Specific Aims**

- We hypothesize that intrathecal morphine will have superior analgesia as demonstrated by charted pain scores and morphine equivalents in the first 24 hours.
- We hypothesize that intrathecal morphine will have higher incidence of side effects when compared to quadratus lumborum blocks

2.0 Background

Postoperatively, abdominal procedures are associated with significant somatosensory pain at the incision site and potential visceral discomfort. Systemic opioid medications were traditionally a critical component for adequate pain control but were also found to be a primary factor contributing to perioperative complications including nausea, vomiting, respiratory depression, and ileus¹.

To reduce systemic opioid administration, regional anesthesia began to play a key role in postoperative pain management for many different types of surgery in children and has done so commonly for at least the last 20 years. A collaborative group of institutions and investigators developed the Pediatric Regional Anesthesia Network to study the practice, risks, and incidence of complications in pediatric regional anesthesia^[9]. This group of 21 centers captures data from every regional technique done for children at these hospitals (including neuraxial techniques like spinals, epidurals, and caudals as well as peripheral nerve blocks and peripheral nerve catheters) and has data on over 100,000 pediatric regional blocks. When looking at their database specifically for complications, they found that there were no incidences of permanent neurologic damage, transient neurologic symptoms occurred in 2.4/10,000 blocks, severe local anesthetic toxicity in 0.76/10,000 blocks, and the most common complications were more benign issues like catheter dislodgement leading to block failure (4%)^[11]. Comparatively, complications were more common in infants less than 6 months old, and this is consistent with other audits of regional anesthetics done by the French-Language Society of Pediatric Anesthesia, where the overall complication rate was found to be less than 0.1% with more prevalence in the less than 6-month-old population^[5]. Further investigations on efficacy of regional anesthesia in pediatric patients has shown decreased need for narcotic pain medications when regional techniques are used. For abdominal surgeries in children, there is no specific standard of care for pain management – just that the anesthetic plan includes a plan for adequate perioperative pain management.

Most abdominal surgeries will have a combination of analgesic modalities with non-steroidal anti-inflammatories and regional anesthesia used to minimize narcotic administration and its associated sedation and side effects. The most common regional techniques used at MUSC for abdominal procedures are intrathecal morphine administration, abdominal wall blocks (including quadratus lumborum blocks), and epidurals. Epidurals also potentially lead to leg weakness (and subsequent patient dissatisfaction) and require increased monitoring at this institution.

Intrathecal morphine has been shown to reduce total opioid consumption for a wide range of pediatric surgical procedures. However, significant rates of pruritis, emesis, and respiratory depression continued to be reported in a dose-dependent manner². Subsequently, low-dose intrathecal morphine (3-5 mcg/kg) was investigated and shown to reduce the incidence of pruritis, emesis, and respiratory depression^[1,4]. Fascial plane blocks have also been used for analgesia in abdominal and thoracic procedures in the

pediatric population to improve pain control and reduce postoperative narcotic administration. Quadratus lumborum blocks specifically provide analgesia for the abdominal wall (incisional pain) as well as some visceral pain relief (i.e., pain related to intraabdominal structures). The purpose of this study is to compare the postoperative analgesia provided by intrathecal morphine to that of bilateral quadratus lumborum blocks for open abdominal procedures.

3.0 Intervention to be studied

- Each of the drugs used in this study have been FDA approved for the adult population. Although not approved for pediatric patients, they are commonly used as part of standard practice for pediatric analgesia and well-studied.
- One group of subjects will receive intrathecal morphine: spinal (neuraxial) dose of preservative free morphine (Duramorph), usually about 4-5mcg/kg. This is injected into the cerebrospinal fluid under sterile technique by a pediatric anesthesiologist while the subject is already under general anesthesia. This procedure is well-described in the pediatric population and used regularly for postoperative pain relief for a variety of procedures including open lower abdominal procedures.
- The second group of subjects will have bilateral quadratus lumborum blocks: peripheral nerve block utilizing ropivacaine 0.2%, usually about $\frac{1}{2}$ mL per/ kg per side (total dose approximately 1mL/kg). This is injected in the subject's flank in the fascial plane between the quadratus lumborum muscle and the psoas muscle. Ultrasound guidance is used for needle and structure localization and this procedure is done by a pediatric anesthesiologist while the subject is already under general anesthesia. Quadratus lumborum blocks are regularly used in clinical practice for postoperative pain relief for a variety of open lower abdominal procedures.

4.0 Study Endpoints

- The primary endpoint will compare the effect that intrathecal morphine and quadratus lumborum blocks have on the duration of analgesia as demonstrated by charted pain scores and morphine equivalents in the first 24 hours.
- The secondary endpoint will assess the side effects of each intervention such as nausea and vomiting, and pruritis. Other secondary endpoints will include patient/family satisfaction, sedation, length of hospital stay, length of PACU stay, and analgesia for hospital stay (as approximated at 48 hours).

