12.0 Data Management

- All data will be kept on a password protected MUSC server and in a REDCap database. All paper data sheets will be kept in a locked cabinet, in a locked office that only IRB approved study team members have access to. Participants will be given a study ID number that will be used to identify them throughout the study.
- The primary outcome of interest is duration of analgesia as demonstrated by morphine equivalents per kg of body weight given in the first 24 hours after surgery.
- Secondary outcomes observed include charted pain scores and reported side effects such as nausea/vomiting or pruritis in the first 48 hours as well as patient/family satisfaction, sedation, length of hospital stay, length of PACU stay, and analgesia for hospital stay, the numerical value for SPO2, SPO2 trend, and use or lack thereof of supplemental O2 in PACU in 15-minute intervals for up to two hours after arrival there.

Demographic and clinical characteristics will be described and compared across the two groups using appropriate statistical tests (Chi-squared tests of homogeneity for categorical variables and t-tests for equality of means, etc.). Significant covariates will be assessed for inclusion in modeling. General linear regression methods will be

used to assess the association of post-surgery MMEs with group (QL vs ITM) adjusted for associated covariates.

Our primary hypothesis is that subjects in the two groups will consume different amounts of post-surgery MMEs. Based on preliminary data from a similar study, we assume that MME/kg consumption in the QL block group will be 0.07 ± 0.076 .

Summary Statements

Assuming a normal underlying distribution, group sample sizes of 12 and 12 achieve 80% power to detect a difference of 0.1 MME/kg between the null hypothesis that both group means are 0.07 and the alternative hypothesis that the mean of group 2 is 0.17 with known group standard deviation of 0.076 and with a significance level (alpha) of 0.05000 using a two-sided Mann-Whitney test. As we anticipate a non-normal distribution, we will inflate sample size by 15%. We will inflate the sample size further by 10% to account for withdrawals.

The final inflated sample size will be 15 per group.

Two-tail test that QL < ITM

$H_0 = \text{Mean}_{QL} = \text{Mean}_{ITM}$

$H_a = \text{Mean}_{QL} \neq \text{Mean}_{ITM}$

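### The primary endpoint differs between sections (pain scores plus opioid use, or 24-hour MME/kg alone), and both versions call it a duration that nothing in the plan measures

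*Combined protocol and SAP*

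**What the plan says.** Three places in the combined protocol and SAP bear on the primary endpoint.

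- **Objectives / Specific Aims (the first section).** The first hypothesis is that "intrathecal morphine will have superior analgesia as demonstrated by charted pain scores and morphine equivalents in the first 24 hours".
- **Section 4.0, Study Endpoints.** The primary endpoint compares the two techniques on "the duration of analgesia as demonstrated by charted pain scores and morphine equivalents in the first 24 hours". Pain scores are not named among the secondary endpoints there, although analgesia over the hospital stay, approximated at 48 hours, is.
- **Section 12.0, Data Management.** The primary outcome is "duration of analgesia as demonstrated by morphine equivalents per kg of body weight given in the first 24 hours" after surgery. The next bullet reads: "Secondary outcomes observed include charted pain scores and reported side effects".

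The rest of Section 12.0 follows its own version. It states: "Our primary hypothesis is that subjects in the two groups will consume different amounts of post-surgery MMEs". The null and alternative hypotheses compare group means. The sample size is built on a difference of 0.1 MME/kg (0.07 against 0.17, SD 0.076). General linear regression is to be "used to assess the association of post-surgery MMEs with group (QL vs ITM) adjusted for associated covariates". No mean, SD, target difference, summary measure or named test is given for pain scores.

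**The concern.** A measure cannot be part of the primary endpoint in one section and secondary in another. Section 4.0 is where a reader looks for the endpoints; Section 12.0 is where the analysis is set out. Either could be cited afterwards as the prespecified primary. In a trial of 30 children the two measures could well disagree, for instance because a child given more opioid may report less pain. The text would then allow the favourable version to be reported as primary.

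Section 4.0 also does not say whether both measures must show a difference or whether one is enough. The two rules have different error rates and different power.

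The label is a separate problem. Sections 4.0 and 12.0 both call the endpoint a duration of analgesia. A duration needs a start, an end event and a rule for children who never reach the event, and none is given. A difference in 24-hour opioid quantity would not support a conclusion that one technique gives longer pain relief.

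**Working it through.** **1. The plan's own figure.** The inputs, all from Section 12.0, are difference 0.1, SD 0.076, two-sided alpha 0.05, 80% power and a Mann-Whitney test.

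- The t-test needs 10.12 per group. Dividing by 0.864, the lower bound for Mann-Whitney efficiency, gives 10.12 / 0.864 = 11.7, so 12 per group.
- Simulated exact Mann-Whitney power under normality at 12 per group is 84%.
- Inflation: 12 × 1.15 × 1.10 = 15.2, or 12 × 1.25 = 15.0.

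The stated 12 and 15 are therefore reasonable, but for MME/kg only. Nothing comparable can be computed for the Section 4.0 endpoint, because no pain-score inputs are given.

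**2. The readings compared.**

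| | Objectives | Section 4.0 | Section 12.0 |
|---|---|---|---|
| Opioid use, 24 h | yes | primary | primary, per kg |
| Pain scores | yes | primary | secondary |
| Called a duration | no | yes | yes |
| Powered and modelled | – | – | MME only |

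**3. Error rates under each reading.** Let Z1 and Z2 be the two test statistics, bivariate normal with correlation r, each tested two-sided at 0.05 (critical value 1.96). The documents give no r, so a range is shown.

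- Section 12.0 alone: nominal 5%.
- Either suffices: 1 − P(|Z1| < 1.96 and |Z2| < 1.96). At r = 0 this is 1 − 0.95² = 0.0975.
- Both required, neither outcome truly different: 0.05 + 0.05 minus the either-suffices value. At r = 0 this is 0.10 − 0.0975 = 0.0025. If one outcome truly differs and the other does not, the bound is 0.05.
- Joint power when both are required: 80% for MME is the stated design target; 80% for pain scores is an assumption. At r = 0 this is 0.80 × 0.80 = 0.64.

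| r | Either suffices: type I error | Both required: type I error | Both required: power |
|---|---|---|---|
| 0 | 9.75% | 0.25% | 64.0% |
| 0.3 | 9.51% | 0.49% | 66.6% |
| 0.5 | 9.07% | 0.93% | 68.7% |
| 0.7 | 8.35% | 1.65% | 71.3% |
| 0.9 | 7.04% | 2.96% | 75.0% |

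If pain-score power is assumed to be 50%, joint power is 40.0% (r = 0) to 49.8% (r = 0.9). If it is assumed to be 90%, joint power is 72.0% to 79.1%.

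**4. The duration label.** Take two children, one given 0.10 MME/kg at hour 2 and the other 0.10 MME/kg at hour 20. Both score 0.10 on the Section 12.0 outcome, although the first needed opioid 18 hours sooner. Comparing group means of this total cannot tell them apart.

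**The case against.** The strongest reply is that Section 12.0 plainly governs. Its named primary outcome, primary hypothesis, sample size and regression all concern MME, and pain scores have no analysis attached anywhere. On that view this is a drafting slip and no result is at risk. The description of Section 12.0 is accurate, and it is why the other sections should be aligned to it. But the plan nowhere says that Section 12.0 prevails, and the section titled Study Endpoints says something else.

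Other points have partial force:

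- Section 4.0 has a secondary 48-hour analgesia endpoint that may include pain scores. That softens the contrast over secondary status, but pain scores remain in its primary endpoint.
- MME/kg over 24 hours is an operational measure, so the variable itself is not missing from Section 12.0. It is still an amount and not a duration.
- The 5% under Section 12.0 is only nominal, since the plan sizes on a Mann-Whitney test, analyses by regression and chooses covariates later. That is accepted.
- The error and power figures rest on assumed correlations and an assumed pain-score power, and they use the 80% design target, although simulated power for MME with all 15 per group evaluable and normal data is about 91%. They show what each reading would imply and are not properties of the trial as enrolled.

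**Conclusion.** The concern holds. The plan contains two incompatible statements of the primary endpoint and no rule for choosing between them, and both carry a label that the measured quantity cannot support. The contradiction needs no assumptions; it is there on the page.

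Its numerical size is conditional. Type I error is nominally 5% under Section 12.0 and at most 5% if both measures are required. It rises to 7.0–9.8% only under an either-suffices rule that the plan does not state. If both are required, power is 64–75% with pain-score power assumed at 80%, and 40–79% with it assumed anywhere from 50% to 90%, for r from 0 to 0.9. The sample size is not wrong for MME/kg.

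The repair is cheap, but it should be made before any unblinded analysis, because it decides which result is the trial's main finding.

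**What to change.** - **Section 4.0:** state one primary endpoint, total MME/kg over 0–24 hours after surgery, tested at two-sided 0.05. Move pain scores to the secondary list with their time window, since Table 2 collects them at 24 and 48 hours.
- **Objectives / Specific Aims:** make the primary hypothesis about MME/kg only, and state pain scores as a separate secondary hypothesis.
- **Sections 4.0 and 12.0:** delete the reference to duration of analgesia from the primary endpoint.
- **Optional:** if duration is of interest, add time to first postoperative opioid dose as a secondary endpoint, with a defined start time and a rule for children who receive none.

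The cost is wording in three sections. There are no extra patients, alpha does not change, and the outcome already powered and modelled stays the same. The optional endpoint needs one timestamp from the medication administration record, which is already being reviewed.

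The alternative of keeping both measures as either/or primaries would cost power. With alpha split to 0.025 each, simulated exact Mann-Whitney power for MME/kg under normality falls from 84% to about 75.5% at 12 per group, and pain scores would still need their own sample-size inputs.

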5.0 Inclusion and Exclusion Criteria/ Study Population

Pediatric patients presenting to undergo ureteral reimplantation surgery will be the study population of interest. Surgery schedules in Epic will be screened for those undergoing this procedure at MUSCs Shawn Jenkins Children's Hospital.

Inclusion Criteria

- Ages 12 months to 11 years old
- Undergoing lower abdominal laparotomy

Exclusion Criteria

- Allergy to morphine or amide local anesthetics
- Localized rash at site of planned regional anesthetic block
- Bleeding diathesis
- Spinal dysmorphism
- Previous spinal surgery with instrumentation of the lumbar spine
- Inability or unwillingness of parent or legal guardian to give informed consent.
- Prior enrollment and randomization in this study

6.0 Number of Subjects

- We will enroll and randomize 30 subjects total.

7.0 Setting

- The study will be conducted at all MUSC preoperative and inpatient locations which includes SJCH, Main (University Hospital), Ashley River Tower, and Rutledge Tower.

8.0 Recruitment Methods

- The study team will refer to the clinic and OR schedules available in Epic to see which patients may qualify. If time allows during the pre-operative clinic visit, the surgeon will briefly introduce the study and provide an informational letter for the patient and family to take home.
- If a potential research subject meets the inclusion criteria, the study team will contact the attending anesthesiologist who will be working the candidate's case to make sure the anesthesia plan does not exclude the patient from the study.
- The patient's parents/guardians will be approached the day of surgery while in pre-op to discuss their willingness to participate in the study.

9.0 Consent Process

Consent will be obtained by IRB approved study team members who have a medical degree and are qualified to discuss the clinical nature of the options being offered.

- As mentioned in the previous section, potential study participants will be informed of the possibility of study participation by their surgeon performing the procedure at the time of discussion of surgery in clinic and be given an informational letter outlining the study. Contact will be made with the child's parent or guardian on the day of the scheduled procedure to discuss the study in greater detail. The study will be explained, and the parent/guardian will be given time to read the consent thoroughly and ask any questions. This will happen in the patient's private room or in the holding area.
- Written informed consent will be obtained if the subject's parent/guardian agrees to participate after the study is thoroughly explained.

- The consent will be obtained in the patient's room or in the private bay in the holding area of MUSC's SJCH.

10.0 Study Design / Methods

- This prospective, randomized, blinded study will attempt to determine if intrathecal morphine provides superior analgesia postoperatively for open lower abdominal procedures when compared to bilateral quadratus lumborum blocks. It will also assess side effects of both pain interventions.
- Once a parent/guardian provide written informed consent, subjects will be assigned a number with a corresponding group. Randomization will be performed by a statistician prior to enrollment and assigned based on the patient's enrollment number. Subjects will be assigned to one of the following groups: 1) Intrathecal Morphine: spinal (neuraxial) dose of preservative free morphine (duramorph), usually about 4-5mcg/kg, or 2) Quadratus Lumborum Block: peripheral nerve block utilizing ropivacaine 0.2%, usually about $\frac{1}{2}$ mL per kg per side (total dose approximately 1mL/kg). The total dose of administered medication (duramorph or ropivacaine) is at the discretion of the anesthesiologist but will be within the dose range as stated above.
- The operating room pharmacist will follow the randomization to prepare or provide the correct medication. Intrathecal morphine will be prepared by the operating room pharmacist. Local anesthetic vials for quadratus lumborum blocks will be obtained from the pharmacy and the medication will be drawn into a syringe by an anesthesiologist who is part of the research team prior to injection. The dosage prepared and administered will be based on weight.
- The pharmacist will not be blinded to the randomization. Nor will the operative team. The study team member who completes data collection from the family and chart review will be blinded to randomization. In addition, the parent and child will also be blinded to the type of block that is used.
- The intervention will be administered in the operating room after the subject is under general anesthesia but prior to incision, as per usual practice. The block will be performed by a study team member board certified in pediatric anesthesiology. Quadratus lumborum blocks are placed using ultrasound guidance, local anesthetic is injected in the fascial plane using aseptic technique. Intrathecal morphine is accomplished by injection of preservative-free morphine in the intrathecal space in the lumbar region using sterile technique.
- Approximately 24 hours after the procedure, a research team member will ask the parent/guardian about side effects such as nausea, vomiting, itching, etc. The research team member will also ask the family if they were satisfied with the subject's pain control postoperatively and overall experience. If a family member or guardian is not present, a care team member will be asked about side effects and the patient's chart will be reviewed for notes pertaining to side effects.
- The patient's chart will be used to see if and how much narcotic pain medication was administered in the first 48 hours after the procedure as well as documented pain scores up to 48 hours after the procedure ends. The chart medication administration record will also be used to identify administration of rescue medications for nausea

or itching non-opioid medications such as acetaminophen or ibuprofen, or other medications such as diazepam or oxybutynin.

Table 1. Baseline and Intraoperative Assessments	
Demographics	
Baseline	
Pre-op meds including opioids in past 24 hours	
Randomization	
Anesthesia intra-op data	
Surgical techniques	
Adverse Events	

Table 2. Post-Op Follow Up Assessments		
Outcome Measure	Instrument	Collected
Pain Scores	Charted pain scores	24 and 48 hrs. post-op
Pain Control Satisfaction	Parent/Guardian Satisfaction	24-hours post-op
Side Effects Experienced	Parent/Guardian Satisfaction	24-hours post-op
Overall Satisfaction	Parent/Guardian Satisfaction	24-hours post-op
Opioid Consumption	MME Consumption	24 and 48 hrs. post-op
Side Effects and Adverse Events	Adverse Events	Assessed through post-op hours 0-48
Medications	Medications used to control or relieve side effects	24 and 48 hrs. post-op

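### Could the outcome collector lose the blind because the plan sets no order between the 24-hour interview and the chart review and names no recorder for Table 1?

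*Combined protocol and SAP*

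**What the plan says.** Section 10.0 assigns blinding by role. The pharmacist and the operative team know the allocation. For outcome collection, "The study team member who completes data collection from the family and chart review will be blinded to randomization". Section 18.0 says the same. Section 10.0 goes on: "In addition, the parent and child will also be blinded to the type of block that is used". The person who gives the intervention belongs to the study team: "The block will be performed by a study team member board certified in pediatric anesthesiology".

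On timing, section 10.0 states: "Approximately 24 hours after the procedure, a research team member will ask the parent/guardian about side effects such as nausea, vomiting, itching, etc". Satisfaction with pain control and with the overall experience is asked at the same contact. There is a fallback: "If a family member or guardian is not present, a care team member will be asked about side effects", and chart notes on side effects are then read as well. The chart supplies opioid use and "documented pain scores up to 48 hours after the procedure ends". In addition, "The chart medication administration record will also be used to identify administration of rescue medications for nausea" or itching.

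Table 1 lists, with no recorder named, a randomization item and "Anesthesia intra-op data". Table 2 puts the three parent/guardian rows at 24 hours, and pain scores, opioid consumption and medications at 24 and 48 hours. No sentence says whether the interview or the chart comes first.

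**The concern.** One role covers both the interview and the chart. Table 2 can be read as placing a first chart extraction at 24 hours, the same time as the interview. A collector who opened the chart first, and found the intrathecal morphine or the ropivacaine block in it, would ask the side-effect questions knowing the arm.

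That matters because the second hypothesis under Objectives / Specific Aims is directional: it expects more side effects with intrathecal morphine. The questions are open, and no structured scale is named, so the way they are put and recorded could shift the answers.

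Two further points add to the worry. If the same collector filled in Table 1, the allocation would be disclosed outright. And in the fallback, the informant is a member of the care team, who is not among those stated to be blinded.

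**Working it through.** The plan gives no figure on this point, so the check sets its statements side by side and counts what is exposed.

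**1. Which outcomes could be affected.** Table 2 has 7 rows:
- 3 from the parent/guardian at 24 hours: pain control satisfaction, side effects experienced, overall satisfaction
- 3 from the chart at 24 and 48 hours: pain scores, opioid consumption, medications
- 1 over hours 0 to 48: side effects and adverse events

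3 + 3 + 1 = 7. The order of interview and chart matters mainly for the first three. Chart entries exist whether or not the collector has yet spoken to the family. The primary outcome in section 12.0, opioid dose per kg over the first 24 postoperative hours, is a chart item. So are the pain scores that section 4.0 places beside it.

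**2. Whether the timing forces a conflict.** The interview is at about 24 hours and the chart window closes at 48 hours: 48 − 24 = about 24 hours. The collection column in Table 2 may name the outcome window or the moment of extraction; the plan does not say. On either reading the interview can come first with no loss of chart data. Section 10.0 also describes the interview before the chart, although it does not make that a rule.

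**3. Who can record the Table 1 items.** A collector who must be blinded to randomization cannot, under that rule, also record randomization. The item therefore falls to someone else. Section 10.0 identifies people who know the allocation, including the study-team anesthesiologist who performs the block. Table 1 names no recorder, but neither does Table 2, so the omission does not single out the allocation item or signal a leak.

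**4. Whether the access rules leak the allocation.** Sections 12.0 and 13.0 limit access to approved team members as a whole and do not separate blinded from unblinded staff. However, the enrollment log in section 13.0 ties study number to patient and is not said to hold the arm.

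**5. The fallback.** It applies only when no family member or guardian is present, and only to side effects; satisfaction questions are not passed to care staff. The plan does not say how often it will be used.

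**6. Scale.** With 15 per group, one child's changed answer moves an arm's rate by 1/15 = 6.7 percentage points. This shows how coarse the comparison is. It does not estimate bias, and the documents offer nothing from which to estimate one.

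**7. Whether tighter rules would gain anything.**
- Having the unblinded anesthesiologist record opioids given between the end of surgery and PACU arrival would move part of the primary outcome from a blinded collector to an unblinded one, in order to protect secondary items.
- Deferring all chart review to 48 hours could delay the finding of adverse events, which Table 2 assesses from hour 0 and section 13.0 requires to be recorded and reported.
- A sensitivity analysis without the fallback cases would select children by family presence, a factor arising after randomization, from about 15 per group.

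**The case for a change.** The strongest reply is that a statement of blinding is an intention, not a procedure. The plan opens the medication record, describes no masked extract, and does not separate blinded from unblinded members in its access rules. Completing the interview first would cost a sentence. Blinded parents lower the risk but do not remove the interviewer's influence, and they are absent in exactly the cases where the fallback applies. Rescue medication is recorded independently of the interviewer, but it does not capture satisfaction or symptoms that went untreated.

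Much of this stands as description. No order is written, no recorder is named, and the care team's blinding status is not given. What does not follow is that the plan as written yields a wrong result. The harm requires that the chart shows the block, that the collector reads it before the interview, and that this knowledge then changes what is asked or recorded. The documents do not establish the first, the plan does not call for the second, and the third cannot be sized. A team that takes its own blinding rule seriously will interview first and have an unblinded colleague enter the allocation.

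**Conclusion.** No change to the plan is needed. Both factual observations are right: the order of interview and chart review is not set, and Table 1 has no named recorder. They concern how a safeguard stated in two sections is carried out, and the blinding rule itself leads a sensible team to fill them the right way. Exposure is limited to 3 of 7 Table 2 rows, all secondary, plus a side-effect fallback of unknown frequency. The usual respondent is a blinded parent or guardian, and the primary opioid outcome is little affected. No sample size, test or error rate depends on the point.

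This rests on two assumptions: that the team honours the collector's blind in practice, and that the fallback is not the main source of side-effect data. Whether the chart reveals the arm remains open. If it does, the order of work on the day matters, and a working instruction to the team can settle that.
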